The FreeStyle Libre Pro Flash Monitoring System is approved by the EMA for people 18 years of age or older with diabetes. The FreeStyle Libre Pro Flash Glucose Monitoring System sensor, which requires 12 to 24 hours to calibrate itself after application, will be worn for 8 days and will record the interstitial fluid glucose every 15 minutes. Data from the 2nd through the 8th days of wear will be used for each analysis. The sensor will be blinded to the subject and no subject action will be needed. The subject will also be issued a Mealtime & Insulin Dose Record in which they will record the time of their meals, and insulin use. After 8 days, the subject may remove the sensor, place in the biohazard bag provided and bring it with them to the randomization visit. If the end of the 8-day continuous glucose monitoring (CGM) period coincides with the date of the randomization visit, the sensor can be removed at the visit. Subjects will bring both their Hypoglycemic Events Record and their Mealtime & Insulin Dose Record to the randomization visit.

Subjects who meet the study eligibility criteria will be centrally randomized 1:1 in an open-label fashion to receive either Gan & Lee Insulin Glargine or Lantus® for 26 weeks.

Randomization will be stratified by country. Subjects will continue using their bolus insulin

but will substitute IP for their basal insulin. The Sponsor will ensure that all insulins will be provided to all subjects regardless of medical insurance or reimbursement issues.

At the randomization visit (Visit 2), subjects will receive supply of insulin kits with IP and the Investigator or designee will train subjects on all study procedures and proper dose administration.

Subjects in both treatment groups will be assessed every 2 weeks after Visit 2 (randomization visit) through Week 22 (telephone call); and then at Week 26; they will attend a total of 9 clinic visits (the screening visit, the randomization visit, and at Weeks 2, 4, 8, 12, 16, 20, and 26), 2 brief visits during which a CGM sensor will be applied (8-10 days before the visits at Weeks 12 and 26), and they will be contacted by telephone at Weeks 6, 10, 14, 18, and 22. The Week 26 visit (Visit 9) will be the end-of-treatment visit.

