**Table 1: Study Procedures and Assessments**

Visit	1	2	3	4	TC	5	TC	--	6	TC	7	TC	8	TC	--	9 a	FU TC
Day or Week	Day -14 thru Day -1	Day 1	Week 2 $\pm$ 3d	Week 4 $\pm$ 3d	Week 6 $\pm$ 3d	Week 8 $\pm$ 3d	Week 10 $\pm$ 3d	Week 11	Week 12 $\pm$ 3d	Week 14 $\pm$ 3d	Week 16 $\pm$ 3d	Week 18 $\pm$ 3d	Week 20 $\pm$ 3d	Week 22 $\pm$ 3d	Week 25	Week 26 $\pm$ 3d	30 days $\pm$ 3d after Visit 9
Informed Consent	X																
Eligibility	X																
Medical History	X																
Randomization	X																
Concomitant Medicationsb	X	X	X	X	X	X	X		X	X	X	X	X	X		X	
Adverse Events	X	X	X	X	X	X	X		X	X	X	X	X	X		X	X j
Vital Signs	X	X	X	X		X			X		X		X				X
Height, Body Weight, BMIc	X	X	X	X		X			X		X		X			X	
Hematology & Chemistryd	X								X								X
Fasting Blood Glucose	X	X	X	X		X			X		X		X			X	
HbA1c	X					X					X					X	
Pre-dose Blood Sample for AIA	X								X								X
Optional Pre-dose PK Blood Sample for Insulin Glargine, M1, M2		X	X	X		X			X		X		X				X
UA, Pregnancy Teste	X	X	X	X		X			X		X		X				X
12-Lead ECG	X																X
Physical Examination	X																X
Glucometer and Supplies Issued, and Training	X																
Apply CGM Sensor and Issue Mealtime & Insulin Dose Recordf	X							X								X	
Collect CGM Sensor and Review Mealtime & Insulin Dose Record		X							X								X
IP and Other Supplies Issuedg		X	X	X		X			X		X		X				
Subject Training on IPh		X															
Review Insulin Use, Glucose Results, & Hypoglycemic Events Recordi		X	X	X	X	X	X		X	X	X	X	X	X		X	
Collect Used Insulin Kits			X	X		X			X		X		X			X	

AIA = anti-insulin antibody; BMI = body mass index; CGM = continuous glucose monitoring; d = Day; ECG = electrocardiogram; HbA1c = glycosylated hemoglobin; IP = investigational product; PK = pharmacokinetic; TC = telephone call; UA - urinalysis

a Any subject who withdraws from the study before Week 26 will perform all study activities scheduled for Visit 9 (EOT visit). Additionally, it is very important for site personnel to encourage subjects to visit the site at Week 26 ( $\pm$  4 weeks) (and Week 12  $\pm$  1 week if applicable) for a blood sample to be obtained for AIA and HbA1c measurements

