#### **8.5.8 Dose Adjustments and Dose Escalation**

The Investigator will develop each subject’s treatment plan and instruct the subject regarding dosing of all their medications, including IP. During the 2-week period between the screening and randomization visits, subjects will have their current basal insulin dose optimized based on fasting glucose results according to **Table 3**. Optimizing the dose before the randomization visit will reduce the need for dose adjustments during the study. Subjects will follow the instructions provided by the Investigator regarding any dose adjustments and other details regarding the clinical management of glucose and insulin.

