### 9.1 Visit 1: Screening: from Day -14 Through Day -1

At the screening visit, subjects will provide informed consent and will be evaluated for eligibility to participate in the study. After the subject signs the ICF, the following information will be collected or procedures performed:

- Eligibility screening
- Adverse events
- Medical history (including diabetes mellitus and thyroid disease history)
- Prior and concomitant medications (including insulin)
- Vital signs, height, body weight, and BMI
- 12-lead ECG
- Physical examination
- Venous blood samples will be collected for the following tests:
  - Routine hematology and chemistry testing including free T4 and TSH (See [Section 10.5](#) for details)
  - FBG test
  - HbA1c
  - AIA (blood should be collected before the subject administers the regular insulin dose)
- Urine samples will be collected for urinalysis and, for women of childbearing potential, a urine pregnancy test
- A capillary blood glucometer, test strips, and other supplies will be issued and the Investigator or designee will provide instruction and conduct training on how to use the glucometer
- The Investigator or designee will apply a CGM sensor and issue an 8-day Mealtime & Insulin Dose Record, and will instruct the subject about the purpose of the CGM, the need to continue performing glucose self-testing with the glucometer, care of the sensor, and how to complete the Mealtime & Insulin Dose Record (subjects will be instructed to bring the record back to their next visit)
- Subjects will also receive a Hypoglycemic Events Record in which they will record information about any hypoglycemic events during their participation in the study
- During the 2-week period between the screening and randomization visits, subjects will have their basal insulin doses optimized as described in [Section 8.5.8](#).

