## 9.2 Visit 2: Randomization (Day 1)

At Visit 2, eligible subjects will be centrally randomized 1:1 in an open-label fashion to receive either Gan & Lee Insulin Glargine Injection or Lantus®. The following information will be collected or procedures performed:

- Concomitant medications and adverse events
- Vital signs, body weight, and BMI
- Venous blood will be collected for the following tests:
  - FBG test
  - Optional PK (blood should be collected before the subject administers the regular insulin dose)
- Urine samples will be collected for urinalysis and, for female subjects of childbearing potential, a urine pregnancy test
- Review of insulin use and glucose results since the previous visit, and the Hypoglycemic Events Record
- The CGM sensor that was applied at the screening visit will be collected (either provided by the subject in a biohazard bag, or removed from arm by the site staff if the end of the 8-day CGM period coincides with the date of the randomization visit)
- The 8-day Mealtime & Insulin Dose Record will be collected and reviewed
- Additional glucose testing supplies will be issued if needed
- IP will be issued
- The Investigator or designee will provide instruction and conduct training on all study procedures and proper dose administration

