7.4 Exploratory

1) Continuous Glucose Monitoring Device Day of Wear

The day of wear will be defined as starting exactly $(x-1)*24$ hours and ending $x*24$ hours after the time of the first assessment at the given visit, where x is the day of wear from 2 to 8 days.

2) Time in hypoglycemia

The time in hypoglycemia will be defined using the CGM data from days 2 through 8 of wear at each of the 3 visits where CGMs are applied as the sum of the time where the glucose value is <3.0 mmol/L.

PPS will be used for some sensitivity analyses (for example, the primary endpoint for immunogenicity [from Section 11.6.1.3] and HbA1c [from Section 11.7.1.3]).

A second Per Protocol Analysis Set (PPS2) will be composed of all subjects whose treatment assignment was randomized, who received at least 1 partial dose and do not have any immunogenicity-interfering important protocol deviations (IIIPD) as defined in Section 11.3 up to visit Week 26. A third Per Protocol Analysis Set (PPS3) will be composed of all subjects whose treatment assignment was randomized, who received at least 1 partial dose and do not have any efficacy-interfering important protocol deviations (EIIPD) as defined in Section 11.3 up to visit Week 26. Subjects in the PPS2 and PPS3 will be grouped according to actual treatment received. The PPS2 and PPS3 are larger and less restrictive analysis sets than the PPS and will be used for some sensitivity analyses for the primary endpoint for immunogenicity [from Section 11.6.1.3] and HbA1c [from Section 11.7.1.3], respectively.

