2. EXCLUSION CRITERIA n. 11	Enrollment of a subject treated with glucocorticosteroids (newly prescribed or high dose), immunosuppressants, or cytostatic agents within 60 days before screening; or treated with a prohibited medication up to randomization.	Yes	11	Yes	Yes

Gan & Lee Pharmaceuticals USA

Sponsor: Gan & Lee Pharmaceuticals USA Corporation
Protocol no.: GL-GLAT1-3001

Statistical Analysis Plan
Version Date: 27-May-2021

Type of Deviation/ Code	Deviation Description	Important protocol deviation	Sub-Category	PD Effect on Immunogenicity	PD Effect on Efficacy
	follow-up procedures; or any other factor that would indicate a significant risk of loss to follow up.				
2. EXCLUSION CRITERIA n. 23	Enrollment of a subject with intolerance or history of hypersensitivity to insulin glargine or any excipient of IP.	Yes	23	Yes	Yes
2. EXCLUSION CRITERIA n. 24	Enrollment of a subject unable or unwilling to wear the CGM sensor as required for the study, or to comply with the concomitant medication requirements in the FreeStyle Libre Pro Indications and Important Safety Information, during the CGM periods.	Yes	24	No	No
3. STUDY DRUG / INVESTIGATIONAL PRODUCT (IP)	Deviations related to study drug				
3. STUDY DRUG	A single dose of study drug is not administered by the subject due to reason(s) other than safety in any given 2-week span during treatment period.	No	1	No	No
3. STUDY DRUG	More than one dose of study drug is not administered by the subject due to reason(s) other than safety in any given 2-week span during treatment period.	Yes	2	No	Yes
3. STUDY DRUG	Subject received the study drug that was assigned to another subject, which is consistent with their assigned treatment.	No	3	No	No
3. STUDY DRUG	Subject received the study drug that was assigned to another subject, which is different than their assigned treatment.	Yes	4	Yes	Yes
3. STUDY DRUG	Subject failed to return the study drug.	No	5	No	No
3. STUDY DRUG	Failure to adjust doses of the study drug according to the instructions provided by the Investigator (especially where doses are expected to have a major impact on outcome) during the treatment period or failure to adjust the previously prescribed basal insulin during the Dose Optimization period.	Yes	6	No	Yes
3. STUDY DRUG	BID dosing of the study drug.	No	7	No	No
3. STUDY DRUG	GCP compliance - Drug Accountability not properly documented by site staff.	No	8	No	No

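### The protocol gives three screening-to-randomization intervals that cannot all hold, and a short gap would lower the baseline CGM total mechanically

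*Protocol*

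**What the plan says.** Three statements in the protocol bear on the same interval.

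- **The label.** The heading of 9.1 is "Visit 1: Screening: from Day -14 Through Day -1", and the day row of Table 1 reads "Day -14 thru Day -1". Randomization is on Day 1 (9.2).
- **The optimization.** 9.1 says "During the 2-week period between the screening and randomization visits, subjects will have their basal insulin doses optimized". 8.5.8 says the same ("During the 2-week period between the screening and randomization visits, subjects will have their current basal insulin dose optimized"), and 8.1 also gives two weeks. No tolerance is attached. Table 3 bases each adjustment on fasting values from 3 days.
- **The sensor.** A CGM sensor is applied at screening and worn for 8 days. 8.1, 8.6.2 and 9.2 allow site staff to remove it at the randomization visit when the wear period ends on that date. 8.1 adds: "Data from the 2 nd through the 8 th days of wear will be used for each analysis".

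For the later sensors (Weeks 11 and 25), 8.6.2, 9.6 and Table 1 footnote f set application 8 to 10 days before the visit. For the baseline sensor no such lead time is given.

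SAP 7.4 defines time in hypoglycemia over wear days 2 to 8 "as the sum of the time where the glucose value is <3.0 mmol/L".

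**The concern.** A site that reads Table 1 as it reads the other columns, as the days on which the visit may fall, could screen a subject a few days before randomization and regard the visit as in window. That gap cannot hold an 8-day wear or a two-week optimization.

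Two things are at stake. First, the outcome is a total and not a fraction of time worn, so a short baseline wear gives a smaller number even when glucose control is unchanged. The Week 12 and Week 26 periods are protected by their lead time, so the change from baseline would then show an increase in hypoglycemia that did not happen. Second, 8.5.8 says that optimizing before randomization is meant to reduce dose adjustment during the study. A shortened interval moves some of that adjustment to after open-label assignment.

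**Working it through.** **Inputs**

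- Screening label: Day -14 to Day -1 (9.1, Table 1).
- Stated interval: 2 weeks (8.1, 8.5.8, 9.1).
- Wear: 8 days. Analysed: wear days 2 to 8, that is 7 days (8.1, SAP 7.4).
- Day of wear: consecutive 24-hour blocks from the first reading (SAP 7.4).
- Fasting data for one adjustment: 3 days (Table 3).
- Study day: Day 1 is the first dose, and earlier dates are the plain date difference, so there is no Day 0 (SAP definition of Study Day).
- Assumption: the first dose is on the randomization day.

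**Step 1: reproduce the plan's own figure.** Screening on Day -k is k days before Day 1. For k = 14 the gap is 14 days, which is the stated 2 weeks. Of the 14 labelled days, only Day -14 gives it.

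**Step 2: compare with the sensor text.** An 8-day wear that starts on Day -k ends on the randomization date only when k = 8. With a fixed gap of 14 days it ends 14 - 8 = 6 days before randomization, so the provision for removal at the visit could never apply. With k = 1 the wear would run 8 - 1 = 7 days past randomization. No single gap satisfies both the 2-week statements and the case of wear ending at the visit.

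**Step 3: consequences if the label is a visit window.**

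- Analysable days = min(8, k) - 1, out of 7.
- Shortfall of the summed baseline at a constant daily rate = 1 - (analysable days)/7.
- Complete non-overlapping 3-day fasting averages = floor(k/3).

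| Screening day | Gap (days) | Analysable CGM days | Shortfall of sum | 3-day averages |
|---|---|---|---|---|
| -14 | 14 | 7 of 7 | 0% | 4 |
| -8 | 8 | 7 of 7 | 0% | 2 |
| -7 | 7 | 6 of 7 | 14% | 2 |
| -5 | 5 | 4 of 7 | 43% | 1 |
| -3 | 3 | 2 of 7 | 71% | 1 |
| -2 | 2 | 1 of 7 | 86% | 0 |
| -1 | 1 | 0 of 7 | no usable data | 0 |

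Days -7 to -1, which are 7 of the 14 labelled days, truncate the CGM baseline. Days -13 to -3 shorten the optimization but leave at least one 3-day average. Only Days -2 and -1 leave none.

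**Step 4: size of the false change.** Let the time in hypoglycemia be d per day throughout. A subject screened on Day -5 has a baseline total of 4d and a full later total of 7d. The ratio is 7/4 = 1.75, an apparent rise of 75% with no true change. As a percentage of sensor time, both periods give the same value.

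**The case against.** The best defence is that the label means a screening period of 14 days and not a window for the visit. Other scheduled clinic visits carry a tolerance of 3 days either way; screening alone is written as a range. The 2-week interval is stated in three places, one of them in the section that carries the label. On that reading the sensor wear and the optimization run side by side and fit. The CGM text also expects the wear to be over by randomization, and 9.2 has the 8-day record collected at that visit. A subject screened on Day -3 would therefore breach other text even if the label allowed it. The Synopsis also bars randomization until eligibility results are confirmed, which makes the shortest gaps less likely.

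Much of this stands: a gap under 8 days is not foreseen, and it is not plainly permitted. The defence does not remove the conflict, because under a fixed 14-day period the wear could not end on the randomization date (Step 2), and no minimum is written.

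On the analysis side, SAP Table 6 places the time-in-range analysis in SAP 11.7.3.2. That section is not in the text available for this review and may already scale to wear time. The CGM endpoints are exploratory and are to be summarized. The gap is fixed before 1:1 randomization, so short wear should fall alike in both arms. These points stand and limit the weight of the finding.

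A reader might also infer that subjects screened in window will be dropped from the PPS and PPS3, because the SAP deviation table lists "failure to adjust the previously prescribed basal insulin during the Dose Optimization period" as important and as affecting efficacy. The documents do not support this. The entry concerns failing to adjust, not a short interval. Table 3 includes a range in which the dose stays unchanged. The same table codes visits outside their window as not important.

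**Conclusion.** The inconsistency holds on either reading of the label. The loss of CGM data holds only if the label is a visit window, the first dose falls on Day 1, and sites use the late part of the window. The documents do not say how many subjects that would be.

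Under those conditions the baseline keeps 6 of 7 analysable days at Day -7, 4 of 7 at Day -5 and none at Day -1. The summed time in hypoglycemia is about 43% low at 4 of 7 days, given a constant daily rate and no scaling elsewhere in the SAP. What suffers is the exploratory comparison of baseline with Weeks 12 and 26 within subjects.

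Two stronger readings are tempting and should not be drawn. One is that subjects could go without any optimization: the arithmetic rules out a complete 3-day average only for screening on Day -2 or Day -1, and for Days -13 to -3 the period is merely shorter. The other is that the main endpoints are compromised: the baseline AIA and HbA1c samples are drawn at the screening visit itself (9.1, Table 1), so a short gap does not lose them, and nothing in the documents quantifies an effect of later titration on the HbA1c comparison.

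**What to change.** 1. **Protocol.** Reconcile the label in Table 1 and 9.1 with the 2-week statements in 8.1, 8.5.8 and 9.1 and with the CGM text in 8.1, 8.6.2 and 9.2. State whether the label is a period or a visit window, and state the minimum interval that governs. The interval also determines how long basal insulin is titrated before randomization, so the choice is the sponsor's and none is proposed here.

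2. **SAP 7.4, and 11.7.3.2 if it does not already do so.** Report time in hypoglycemia and time in hyperglycemia as a percentage of valid sensor time on wear days 2 to 8. Keep a duration in minutes for each event, because the one-hour rule for persistent hypoglycemia in SAP 7.3 refers to the 7.4 definition and cannot be applied to a percentage.

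The cost is minor wording and programming work, with no added visit. Depending on the interval chosen, some subjects may wait longer for randomization. The second change is useful whatever the sponsor decides on the first, since it also protects against early sensor loss at any visit.

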## 9.2 Visit 2: Randomization (Day 1)

At Visit 2, eligible subjects will be centrally randomized 1:1 in an open-label fashion to receive either Gan & Lee Insulin Glargine Injection or Lantus®. The following information will be collected or procedures performed:

- Concomitant medications and adverse events
- Vital signs, body weight, and BMI
- Venous blood will be collected for the following tests:
  - FBG test
  - Optional PK (blood should be collected before the subject administers the regular insulin dose)
- Urine samples will be collected for urinalysis and, for female subjects of childbearing potential, a urine pregnancy test
- Review of insulin use and glucose results since the previous visit, and the Hypoglycemic Events Record
- The CGM sensor that was applied at the screening visit will be collected (either provided by the subject in a biohazard bag, or removed from arm by the site staff if the end of the 8-day CGM period coincides with the date of the randomization visit)
- The 8-day Mealtime & Insulin Dose Record will be collected and reviewed
- Additional glucose testing supplies will be issued if needed
- IP will be issued
- The Investigator or designee will provide instruction and conduct training on all study procedures and proper dose administration

## 9.3 Visits 3 and 4: Weeks 2 and 4 ( $\pm 3$ Days)

At each clinic visit, the following information will be collected or procedures performed:

- Concomitant medications and adverse events
- Review of IP and bolus insulin use, glucose results, and the Hypoglycemic Events Record
- Vital signs, body weight, and BMI
- Venous blood will be collected for the following tests:
  - FBG test
  - Optional PK (blood should be collected before the subject administers the regular insulin dose)
- Urine samples will be collected for urinalysis and, for female subjects of childbearing potential, a urine pregnancy test
- IP and other supplies will be issued if needed, and any used insulin kits will be collected for accountability

## 9.4 Telephone Contacts: Weeks 6, 10, 14, 18, and 22 ( $\pm 3$ Days)

At these weeks, the Investigator or designee will call the subjects and collect information about concomitant medications, adverse events, use of IP and bolus insulin, and glucose

results. The subject will be asked about any hypoglycemic events and ensure that they have been recorded in the Hypoglycemic Events Record.

### **9.5 Visit 5: Week 8 (± 3 Days)**

At this visit, the following information will be collected or procedures performed:

- Concomitant medications and adverse events
- Review of IP and bolus insulin use, glucose results, and the Hypoglycemic Events Record
- Vital signs, body weight, and BMI
- Venous blood will be collected for the following tests:
  - FBG test
  - HbA1c
  - Optional PK (blood should be collected before the subject administers the regular insulin dose)
- Urine samples will be collected for urinalysis and, for female subjects of childbearing potential, a urine pregnancy test
- IP and other supplies will be issued if needed, and any used insulin kits will be collected for accountability

